3. STUDY DESIGN

AI-STROKE is an investigator-initiated, multicenter, diagnostic test accuracy study.

PART A: ALGORITHM DEVELOPMENT AND VALIDATION IN THE PREHOSPITAL SETTING

This part is carried out by two ambulance services (Ambulance Amsterdam and Ambulance Noord-Holland Noord). These ambulances almost exclusively transport suspected AIS patients to the following hospitals: AMC, VUMC, OLVG West and Noordwest Ziekenhuisgroep, location Alkmaar. The ambulance services and these hospitals are therefore all participating centers in this study. A single EEG will be performed in patients with a suspected AIS as assessed by the ambulance paramedic, or with a radiologically confirmed LVO (in case of transport to an EVT center). The acquired data will be used for development and validation of one or more AI-algorithms for LVO-detection and validation of existing EEG-algorithms.

PART B: ALGORITHM DEVELOPMENT AND VALIDATION IN THE EMERGENCY ROOM

This part is carried out in the emergency room (ER) of AMC. A single EEG will be performed in patients with a suspected AIS as assessed by the ambulance paramedic that presents the patient to the ER, or with a radiologically confirmed LVO and who are transported to the AMC for EVT. We will use the data for training and validation of one or more AI-algorithms for LVO-detection and validation of existing EEG-algorithms.

At the start of the study, EEG data of suspected AIS patients will be limited. In this phase, we will use existing fully anonymized EEG data, obtained as part of standard medical care, and data from the ELECTRA-STROKE study for pretraining of the AI-algorithms (see chapter 10).

In both study parts a single EEG is performed. After informed consent is given, information is collected on patient characteristics, medical history, medication use, physical and neurological examination performed by the treating physician, imaging studies, diagnosis and treatment as well as logistical and technical information, obtained from the patient, the treating physician and the Emergency Medical Service (EMS). There are no follow up visits.

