4.2 INCLUSION CRITERIA

PART A AND B

All subjects must meet all of the following criteria:

- Suspected AIS, as assessed by the attending ambulance paramedic, or a known LVO stroke;
- Onset of symptoms or last seen well < 24 hours before EEG acquisition;
- Age of 18 years or older;
- Written informed consent by patient or legal representative (deferred).

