4.4 SAMPLE SIZE CALCULATION

We aim to develop and validate a novel algorithm for diagnosis of LVO stroke. In the prehospital and inhospital setting together, EEG-measurements will be performed in a maximum of 1192 patients.

Using preliminary data of the ongoing ELECTRA-STROKE study (clinicaltrials.gov, NCT03699397), we identified two independent EEG predictors for LVO stroke: the theta-alpha ratio and the weighted phase lag index. For optimal algorithm development, using conventional statistical methods, 20-50 events (i.e. LVO strokes) per predictor are required in the derivation cohort.³⁰ Thus, with conventional statistics, 40-100 patients with an LVO stroke would be required for algorithm development. Based on an incidence of 12% for LVO stroke among patients with a suspected AIS³¹, and assuming a dropout rate of 30% (either due to missing consent or failed EEG registration), 484-1192 patients with a suspected AIS are required.

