8.5 REPLACEMENT OF INDIVIDUAL SUBJECTS AFTER WITHDRAWAL

Since our sample size calculation includes an expected dropout rate, we do not intend to replace subjects that have withdrawn from the study. However, if the drop-out rate is higher than anticipated or when the number of LVO stroke patients is lower than expected, the steering committee (as specified in Appendix

7) may decide on replacement at a later stage. Records will be kept of all reasons for withdrawal and these will be reported along with the study results.

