EEG data quality will be monitored continuously to avoid an excessive drop-out rate due to malfunctioning EEG hardware. Two interim analyses for the AI algorithms will be performed: the first when 50 and the second when 100 LVO stroke patients are included in the study. Results of these analyses will be obtained by performing k-fold cross-validation on the training data, including data from the ER and the ambulance. The diagnoses (i.e. LVO stroke or no LVO stroke) as predicted by the developed algorithms will be compared to the diagnoses given by the adjudication committee. A receiver operating characteristic (ROC) curve will be plotted for each algorithm and the optimal cut-off value (i.e. highest sensitivity at a specificity \geq 80%) for each algorithm will be determined. For these cut off values, the sensitivity, specificity, negative predictive value and positive predictive value will be reported, including 95% confidence intervals. The steering committee may decide to prematurely stop the recruitment in the study if the results of the interim analysis show that an accurate and stable algorithm can be developed with the data collected up till that point.

Eventually, we will evaluate the performance of the developed classification algorithm(s) and several existing algorithms on the validation data set. A receiver operating characteristic (ROC) curve will be plotted for each algorithm and the optimal cut-off value (i.e. highest sensitivity at a specificity \geq 80%) for each algorithm will be determined. For these cut off values, the sensitivity, specificity, NPV and PPV value will be calculated.

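### The interim looks and the LVO-shortfall rule pool LVOs already known at enrolment with LVOs found among suspected-AIS patients, although the 1192 and the objective rest on suspected AIS

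*Combined protocol and SAP*

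**What the plan says.** Section 4.2 opens two routes into the study: "Suspected AIS, as assessed by the attending ambulance paramedic, or a known LVO stroke". Section 3 describes the second route in both parts. Part A takes confirmed LVOs being moved to an EVT center, and Part B takes patients "or with a radiologically confirmed LVO and who are transported to the AMC for EVT". Section 2 states the objective for patients with a suspected AIS in the prehospital setting.

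Section 4.4 asks for 40 to 100 LVO strokes for algorithm development and converts them to patient numbers as follows: "Based on an incidence of 12% for LVO stroke among patients with a suspected AIS", with 30% dropout. This gives 484 to 1192. There is no term for known-LVO entrants.

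Section 10 times the interim analyses by LVO count, "the first when 50 and the second when 100 LVO stroke patients are included in the study", and obtains their results by "performing k-fold cross-validation on the training data, including data from the ER and the ambulance". On stopping it says: "The steering committee may decide to prematurely stop the recruitment in the study if the results of the interim analysis show" enough accuracy and stability from the data in hand. Section 8.5 lets the committee consider replacement "when the number of LVO stroke patients is lower than expected". Neither rule mentions route of entry. No section forecasts, caps or separately analyses known-LVO patients.

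**The concern.** A patient enrolled because the LVO is already confirmed adds one LVO to the count with near certainty. At the planning yield, one LVO among suspected-AIS patients takes about eight evaluable patients (1/0.12 = 8.3). Counting both alike lets the looks arrive earlier, and with fewer target-population LVOs, than the 12% yield implies.

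The larger issue is the results the committee sees. Known LVOs add cases but no non-cases. They raise the prevalence in the pooled data, which raises PPV and lowers NPV. They also enter sensitivity and the AUC, although their LVO status is not in question and they lie outside the triage problem that the algorithm is meant to solve. Specificity is essentially unaffected, because the non-LVO patients come from the suspected-AIS route. The committee would therefore judge accuracy and stability partly on the wrong population. A pooled count could also make a low yield among suspected-AIS entrants harder to see.

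**Working it through.** **Inputs.** From section 4.4: 40 to 100 events, 12% LVO among suspected AIS, 30% dropout, maximum 1192. From section 10: looks at 50 and 100 LVOs. From section 1: about 7% LVO among suspected AIS. Assumed, because the documents give no figure: known-LVO share *k* = 5%, 10% or 20% of evaluable patients, all confirmed on adjudication, and looks counted in evaluable patients.

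**1. The plan's own figure.** N = (events / 0.12) / 0.70, rounding up at each step.
- 100 events: 100/0.12 gives 834; 834/0.70 gives 1192, as stated.
- 40 events: 40/0.12 gives 334; 334/0.70 gives 478, against 484 stated (about 1% apart).
- Back-check: 1192 × 0.70 × 0.12 = 100.1 LVOs.

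The maximum is thus expected to yield 100 LVOs with no known-LVO entrants at all.

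**2. Content and timing of the 100-LVO look.** LVOs per evaluable patient = *k* + 0.12(1 − *k*). Suspected-AIS share of LVOs = 0.12(1 − *k*) divided by that.

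| *k* | LVOs per evaluable patient | Suspected-AIS LVOs among 100 | Evaluable patients at 100 LVOs |
|---|---|---|---|
| 0 | 0.120 | 100 | 833 |
| 5% | 0.164 | 0.114/0.164 → 70 | 610 |
| 10% | 0.208 | 0.108/0.208 → 52 | 481 |
| 20% | 0.296 | 0.096/0.296 → 32 | 338 |

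The 50-LVO look halves every count: about 35, 26 or 16 suspected-AIS LVOs.

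**3. Effect on PPV.** Take sensitivity = specificity = 0.80, for illustration only. PPV = 0.8*p* / (0.8*p* + 0.2(1 − *p*)).
- *p* = 0.12: 0.096 / (0.096 + 0.176) = 35%.
- *p* = 0.208 (*k* = 10%): 0.1664 / (0.1664 + 0.1584) = 51%.

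The algorithm is identical in both lines; only the case mix differs.

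**4. Visibility of a shortfall.** Evaluable patients at the maximum: 1192 × 0.70 = 834. At a 7% yield, with no known LVOs, 834 × 0.07 = 58 LVOs. The number *x* of known LVOs that brings the total to 100 solves *x* + 0.07(834 − *x*) = 100, so *x* = (100 − 58.4)/0.93 = 45, or 5.4% of evaluable patients. About 55 LVOs would then come from suspected AIS. Judged by route, the remaining 789 or so suspected-AIS patients would be expected to give 789 × 0.12 = 95 LVOs, and the gap between 55 and 95 would be plain.

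**The case against.** Several stronger readings are tempting, and the documents do not support them.

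- **That the looks will hold about half the intended LVOs.** This is one scenario. The enrolled known-LVO share is not given. Section 1 says that about half of EVT-eligible patients first reach a hospital without EVT, but that is not the share in question. Section 3 enrols each patient once, so a transferred patient already recorded on the first ride is not added again.
- **That reaching the count stops the study.** It starts an analysis. Stopping also needs favourable results and a committee decision, and section 3 lets the committee stop early on the same ground without naming a count.
- **That section 8.5 is disabled.** It has no threshold: the expected number is undefined and replacement is discretionary. A pooled count can obscure a shortfall, but nothing prevents the committee from looking by route.
- **That section 4.4 requires 40 to 100 LVOs from suspected-AIS entrants.** Its requirement is worded as LVO strokes of any route, for derivation. The restriction enters only through the 12% conversion. Known LVOs are legitimate training events, and at shares of 5% or 10% the second look still holds more than 40 suspected-AIS LVOs. The link from 50 and 100 to section 4.4 is itself an inference: 100 matches the upper bound, while 50 is not a total stated there.
- **That a planned number of validation LVOs is lost.** The plan states only an 80/20 split and sets no event count for validation.

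These points limit the claim about counts. They do not answer the point about results: the performance estimates that inform stopping are pooled over both routes, while the objective concerns one of them.

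**Conclusion.** The concern holds as a mismatch of populations. The 1192 is built on the yield among suspected AIS and the objective concerns suspected AIS, but the interim results and the shortfall rule include known LVOs without distinction. The direction is certain at any non-zero known-LVO share: earlier looks, fewer target-population LVOs, higher PPV and lower NPV. The size is not known. Over assumed shares of 5% to 20%, the 100-LVO look holds about 70 to 32 suspected-AIS LVOs. The PPV contrast of 51% against 35% rests on a 10% share and on the illustrative 80% sensitivity and specificity. The masking example rests on the 7% yield in section 1 and an assumed 45 known-LVO patients. How far pooling shifts sensitivity or the AUC cannot be computed from the documents. The matter should be settled before the first look; it does not undermine the use of known LVOs for training.

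**What to change.** Keep the looks at 50 and 100 LVOs and keep known LVOs for training. Then:

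- **Section 10:** compute the cross-validated AUC, sensitivity, specificity, PPV and NPV that inform the stop decision on held-out patients who entered as suspected AIS only. Show the committee the LVO count by entry route at each look.
- **Section 8.5:** judge whether LVOs are fewer than expected among suspected-AIS entrants, against 12% of the evaluable patients who entered by that route.

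Counting only suspected-AIS LVOs toward the looks is not advised. At the maximum, the expected number is 1192 × 0.70 × 0.12 × (1 − *k*) = 95, 90 or 80 at shares of 5%, 10% or 20%, so the second look would not be expected within the cap.

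**Cost:** fewer events and wider intervals at each look. For sensitivity the width grows roughly as the square root of the ratio of events: √(100/70) = 1.2, √(100/52) = 1.4 or √(100/32) = 1.8 times at the three shares. Entry route must also be recorded for each patient. Section 8.3 lists no such field, but already collects transfer times from another hospital, so the addition is small.

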10. ALGORITHM DEVELOPMENT AND STATISTICAL ANALYSIS

ALGORITHM DEVELOPMENT

The EEG data obtained in the prehospital setting and in the ER will be divided in a training (80%) and validation (20%) set. Only the training set will be used to train novel AI-algorithms for LVO-detection. First, we will create a logistic regression model based on standard EEG-features, e.g. time domain characteristics, power spectral density in different frequency bands, coherence measures, and entropy measures. This model will be the reference to assess the improvement of the other novel AI-based models. We plan to base the final AI-STORKE algorithm on artificial neural networks, but other EEG classification algorithms (e.g. based on support vector machines and random forests) may be explored as well.³⁴ First, we will create convolution neural networks (CNN's) using the extracted EEG-features. Subsequently, we will evaluate whether the EEG-signals contain more information than these features by creating models that analyze the time series directly. To deal with the different timescales of features in EEG-signals and their dynamic behavior, we aim to study recurrent neural networks (RNN's). Examples of such RNN's include Long Short-Term Memory (LSTM)^{35, 36}, Gated Recurrent Unit (GRU) CNN's, and Deep Belief networks (DBN's)³⁷. The first models will be built using a limited set of EEG data since data collection is part of this study. We will deal with the data sparsity using two approaches: (I) Transfer learning, we will train models for other EEG classification tasks (such as classification of stroke vs. healthy subjects or male vs. female), so that features from the time signals are trained. For this, existing fully anonymized EEG data will be used. The trained models will subsequently be used to fine-tune the classification of suspected AIS patients. (II) Reinforcement learning³⁸, and uncertainty-based learning in particular. We will update the models by feeding the data that are collected during the study. During the EEG data collection, the algorithm will be evolving, and the correct classification ratio will be improving as more data are added. The final algorithm will be considered successful if an AUC of >0.80 is reached in the validation set.

STATISTICAL ANALYSIS

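### Interim and final performance is pooled over ER and ambulance EEGs with no by-setting result, so it can misstate accuracy in prehospital suspected AIS

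*Combined protocol and SAP*

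**What the plan says.** The objective (chapter 2) is to identify LVO in suspected AIS in the prehospital setting, and section 8.1.2 lists prehospital accuracy among the secondary end points.

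Chapter 10 pools the settings at both stages. For the split: "The EEG data obtained in the prehospital setting and in the ER will be divided in a training (80%) and validation (20%) set". For the interims, the results come from "k-fold cross-validation on the training data, including data from the ER and the ambulance". The looks come "the first when 50 and the second when 100 LVO stroke patients are included in the study". ROC curve, cut-off (highest sensitivity with specificity of at least 80%), sensitivity, specificity, PPV and NPV are specified per algorithm. No result by setting, no stratified fold and no adjustment for setting is described.

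On stopping: "The steering committee may decide to prematurely stop the recruitment in the study", provided the results show that "an accurate and stable algorithm can be developed with the data collected up till that point". Neither a numerical threshold nor a setting is attached. The AUC criterion of more than 0.80 applies only to the final validation set.

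On the settings (chapter 3): Part A is recorded by two ambulance services. Of Part B the plan says "This part is carried out in the emergency room (ER) of AMC". Both parts also admit patients with a confirmed LVO on their way to EVT. Chapter 10 further plans "creating models that analyze the time series directly", so the models are not restricted to predefined features.

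**The concern.** A pooled AUC compares every LVO patient with every non-LVO patient, including pairs from different settings. Suppose one setting has a higher LVO share and the model can partly tell the settings apart, through signal quality, environment or time since onset. It then gains by scoring that setting higher. Pairs with the LVO patient in the richer setting are favoured and the opposite pairs are penalised. With unequal shares the favoured pairs are more numerous, so the net effect is upward.

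Inside an ambulance the setting is constant and this gain disappears. The committee could therefore judge accuracy on a figure that does not apply where the algorithm is to be used. The final validation set would not reveal the problem, because it is mixed in the same way. The cut-off is affected too: one threshold set on pooled data sits at different points of the ROC curve in each setting.

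**Working it through.** **The plan's own figure.** No interim performance figure is given. The only related number is the sample size in section 4.4: 100/0.12 gives 834, and 834/0.70 gives 1192, as stated. The lower end, 40/0.12 = 334 and 334/0.70 = 478, is close to the stated 484. Conversely, 1192 × 0.70 × 0.12 ≈ 100 LVO, so the second look falls at about full recruitment if LVO patients are counted after dropout.

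**Inputs from the documents.** LVO share in suspected AIS of 12% (section 4.4) or about 7% (chapter 1), used here for Part A; specificity of at least 80%; 80% training split; first look at 50 LVO.

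**Assumptions.** Part B is a fraction f = 30-50% of patients with an LVO share pE of 20-40%. The true AUC is 0.75 within each setting (binormal). The model recognises the setting perfectly and uses it optimally, which makes the results an upper bound.

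**Formulas.** With pA the Part A share:
- a = P(ER | LVO) = f·pE / [f·pE + (1−f)·pA]
- b = P(ER | no LVO) = f(1−pE) / [f(1−pE) + (1−f)(1−pA)]
- AUC of setting alone = 0.5 + 0.5(a − b)
- d = √2·Φ⁻¹(0.75) = 0.954, and shift s = [logit pE − logit pA]/d
- Pooled AUC = [ab + (1−a)(1−b)]·0.75 + a(1−b)·Φ((d+s)/√2) + (1−a)b·Φ((d−s)/√2)

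**Worked case** (f = 30%, 12% versus 30%). a = 0.090/0.174 = 0.517; b = 0.210/0.826 = 0.254; s = 1.145/0.954 = 1.201. Pooled AUC = 0.4915 × 0.75 + 0.3857 × 0.936 + 0.1227 × 0.431 = 0.78.

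| LVO share, Part A / Part B | Setting alone (f = 30%, 50%) | Pooled AUC (f = 30%, 50%) |
|---|---|---|
| 12% / 12% | 0.50, 0.50 | 0.75, 0.75 |
| 12% / 20% | 0.57, 0.57 | 0.76, 0.76 |
| 12% / 30% | 0.63, 0.64 | 0.78, 0.78 |
| 12% / 40% | 0.68, 0.68 | 0.81, 0.81 |
| 7% / 30% | 0.70, 0.69 | 0.82, 0.82 |
| 30% / 12% (reversed) | 0.60, 0.64 | 0.78, 0.78 |

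The ambulance AUC is 0.75 in every row. With Part B at only 10-20% of patients, the 12%/30% case gives 0.77-0.78.

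**Cut-off at 12% versus 30%.** Find c such that b·Φ(c−s) + (1−b)·Φ(c) = 0.80.
- f = 30%: c = 1.254. Ambulance sensitivity = 1 − Φ(1.254 − 0.954) = 38%; ER sensitivity = 82%; pooled = 0.517 × 0.816 + 0.483 × 0.382 = 61%. Ambulance specificity = Φ(1.254) = 90%.
- f = 50%: c = 1.528. Ambulance sensitivity 28%; pooled 0.714 × 0.735 + 0.286 × 0.283 = 61%. Ambulance specificity 94%.
- Equal shares: c = 0.842 and sensitivity is 54% in both settings.
- Reversed shares (Part A 30%, Part B 12%): c = 0.563 (f = 30%) and 0.327 (f = 50%). Ambulance sensitivity is 65% and 73%, but ambulance specificity is Φ(c) = 71% and 63%, below the 80% that the rule is meant to hold.

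**Precision of a Part A figure at the first look.** Training holds 0.80 × 50 = 40 LVO. At 12% versus 30%, Part A has 40 × 0.483 ≈ 19 (f = 30%) or 40 × 0.286 ≈ 11 (f = 50%), with 19.3 × 0.88/0.12 ≈ 142 or 11.4 × 0.88/0.12 ≈ 84 non-LVO. The Hanley-McNeil standard error at AUC 0.75 is 0.067 or 0.087, so the 95% half-width is 0.13 or 0.17.

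**The case against.** - **Direction.** A reader might infer that the ER is the LVO-richer setting because patients are brought there for EVT. The documents do not support this: Part A also enrols confirmed LVO during transport to an EVT center, and a patient recorded there gets no second EEG in Part B (chapter 3). This objection stands. It does not remove the point, because unequal shares in either direction suffice.
- **Recognition of setting.** Section 7.1 describes one cap, amplifier and acquisition software. That a network can tell the settings apart is plausible, not shown. The figures above are therefore a ceiling.
- **Size.** Even at that ceiling the AUC inflation is 0.01 at 20% LVO in Part B and about 0.03 at 30%. Passing 0.80 needs 40% against 12%, or 30% against 7%. This stands for the AUC; the distortion at the cut-off is larger.
- **Stopping.** A reader might infer that the pooled AUC would trigger an early stop. It would only inform one: the decision is discretionary, also requires stability, and has no AUC threshold. By the plan's own arithmetic only the first look could save much recruitment.
- **Prehospital end points.** Section 8.1.2 already asks for prehospital accuracy. That supports an ambulance-only analysis, but chapter 10 does not plan one.
- **A Part A-only stop rule.** With 11-19 LVO at the first look, the half-width is several times the AUC bias. Resting the decision on that figure alone is a trade-off and is not recommended here.

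**Conclusion.** The omission is certain: the figures that inform stopping, and those that decide final success, come from pooled settings, while the target is prehospital suspected AIS. The size of any resulting error is unknown, because the plan gives neither LVO share nor number of patients by part.

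Under perfect recognition of setting, a true AUC of 0.75 and Part B at 30-50% of patients, the pooled AUC lies between 0.75 (equal shares) and about 0.82 (7% versus 30%). At 12% versus 30%, the reported sensitivity of about 61% corresponds to 28-38% in the ambulance, at an ambulance specificity of 90-94%. Partial recognition would give less.

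It would go too far to say that every pair of an ER LVO patient and an ambulance non-LVO patient counts as correct. That holds only for a score made of setting alone; in the scenarios with the ER richer, 87-98% of such pairs are ranked correctly, against 75% without the shortcut. Nor do the documents show that ambulance AUC will be far below the pooled figure. They show that the plan has no means of seeing whether it is. This is a worthwhile, inexpensive correction to chapter 10.

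**What to change.** Amend chapter 10 as follows.
- At each interim (out-of-fold predictions) and in the final validation, report AUC, and sensitivity and specificity at the chosen cut-off, separately for Part A and Part B. Within Part A, report them for suspected AIS without known-LVO transfers, since Part A itself mixes the two groups.
- Report the AUC of a model that uses setting alone, as a reference for how much the pooled figure could owe to setting.
- Give the steering committee the ambulance suspected-AIS figure with its 95% confidence interval beside the pooled figure. State that no algorithm is called accurate on the pooled figure alone.
- Report patient numbers and LVO shares by part at each look.

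The cost is wording and a stratified table of predictions that already exist; no new data are needed. The drawback is precision: about ±0.13-0.17 on the Part A AUC at the first look under the assumptions above, and wider once known-LVO transfers are removed. The validation set is smaller still: of 100 LVO it would hold 20, of which about 20 × 0.483 ≈ 10 or 20 × 0.286 ≈ 6 in Part A. Those intervals show how much information the study has on its target setting.

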1. INTRODUCTION AND RATIONALE

Acute ischemic stroke (AIS) is a major cause of death and disability worldwide.^{13, 14} Large vessel occlusion (LVO) stroke causes around 30% of AIS and is associated with more severe deficits and worse neurological outcomes than other types of AIS.¹⁻⁴ In 2015, endovascular thrombectomy (EVT) became standard treatment for patients with LVO stroke. EVT improves the chance of good functional outcome in patients with an LVO, provided it is initiated within 6 hours, or in a selected population, within 24 hours after stroke symptom onset.¹⁵⁻¹⁷ Early initiation of EVT within these time-ranges is extremely important, as each 9minute delay results in a poor functional outcome in 1 of every 100 treated patients.¹⁸ However, EVT is a complex procedure that can be performed in specialized hospitals only, so-called comprehensive stroke centers. In the Netherlands, approximately half of EVT-eligible patients are initially admitted to a hospital where this therapy is not available, and are – once it has been established that they are eligible for EVT - transferred to an EVT-capable hospital.⁵ In other countries this proportion is even higher. In the Netherlands, this interhospital transfer delays treatment with about 1 hour and leads to an decrease in the absolute chance of functional independence of the patient by 5-15%.⁵⁻⁷ Direct presentation of all suspected AIS patients to an EVT-capable hospital, however, is also not feasible, since only approximately 7% of these patients have an LVO. Therefore, a prehospital triage instrument that reliably identifies LVO stroke patients allowing direct transport to an EVT capable hospital, is much needed.

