2. OBJECTIVES

The primary objective of this study is to develop one or more novel AI-based algorithms (the AI-STROKE algorithms) with optimal diagnostic accuracy for identification of LVO stroke in patients with a suspected AIS in the prehospital setting, based on ambulant EEG data.

The secondary objectives are:

- Assessing the diagnostic accuracy of existing EEG algorithms for identification of LVO stroke in patients with a suspected AIS in the prehospital setting;
- Improving the applicability and reliability of the dry electrode EEG cap for use in the prehospital setting;
- Assessing the logistical and technical feasibility of ambulance paramedics performing ambulant EEGs, using an improved dry electrode EEG cap, in the prehospital setting in patients with a suspected AIS.

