8.1.2 SECONDARY STUDY PARAMETERS/END POINTS

Secondary end points of this study are:

- AUC, sensitivity, specificity, positive predictive value (PPV) and negative predictive value (NPV) of the AI-STROKE algorithms based on ambulant EEG for diagnosis of LVO of the anterior circulation in suspected AIS patients in the prehospital setting;
- AUC, sensitivity, specificity, PPV and NPV of existing EEG algorithms based on ambulant EEG for diagnosis of LVO of the anterior circulation in suspected AIS patients in the prehospital setting;
- AUC, sensitivity, specificity, PPV and NPV of existing and newly developed EEG algorithms based on ambulant EEG for detection of LVO stroke of the posterior circulation, intracerebral hemorrhage, transient ischemic attack, and stroke mimics;
- Technical and logistical feasibility (e.g. in terms of EEG channel reliability) of paramedics performing ambulant EEG in patients with a suspected AIS in the prehospital setting.

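### Existing EEG algorithms are tested only on the 20% validation set, although for any not tuned on study data every Part A suspected-AIS patient is valid test data; the cost is precision, not bias

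*Combined protocol and SAP*

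**What the plan says.** Chapter 10 describes the split: "The EEG data obtained in the prehospital setting and in the ER will be divided in a training (80%) and validation (20%) set". It does not say whether the split is stratified by setting. The larger part has one stated training use: "Only the training set will be used to train novel AI-algorithms for LVO-detection". No section trains or tunes existing algorithms on study data, and none names them.

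For the final evaluation, chapter 10 says that "we will evaluate the performance of the developed classification algorithm(s) and several existing algorithms on the validation data set". It does not restrict this to the Part A patients in that set. The operating point comes from the evaluation data: "A receiver operating characteristic (ROC) curve will be plotted for each algorithm and the optimal cut-off value", meaning the highest sensitivity at a specificity of at least 80%, is derived for each algorithm from its curve.

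The existing algorithms have an objective of their own, the first secondary one in chapter 2: "Assessing the diagnostic accuracy of existing EEG algorithms for identification of LVO stroke in patients with a suspected AIS in the prehospital setting". The matching end point in section 8.1.2 lists the AUC and four measures that depend on a cut-off (sensitivity, specificity and the two predictive values), describing the performance "of existing EEG algorithms based on ambulant EEG for diagnosis of LVO of the anterior circulation in suspected AIS patients in the prehospital setting". Both concern the prehospital setting, which is Part A.

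Chapter 3 says in general terms that the acquired data will serve to validate existing algorithms, and sets no 20% limit. Section 4.2 admits patients with "Suspected AIS, as assessed by the attending ambulance paramedic, or a known LVO stroke", so Part A may also hold patients whose LVO was already established.

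**The concern.** The 80/20 split exists because a fitted model looks better on the data it was fitted to. That reason applies to the AI-STROKE algorithms. It does not apply to an algorithm fixed before the study, for which the training-set patients are as much unseen data as the validation-set patients. Their EEGs and adjudicated diagnoses will already have been collected.

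What is at stake is how precisely the study answers its first secondary objective. LVO is the minority class, and a fifth of the data may contain few LVO cases from the ambulance. An AUC interval running from the low 0.60s to the high 0.90s would not separate a weak triage tool from a very good one. An additional analysis is not excluded, but chapter 10 describes none. One chosen after the results are known would carry less weight than one written down now.

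**Working it through.** **Inputs from the documents.** Maximum enrolment 1192, dropout 30% and LVO incidence 12% (section 4.4); split 80/20 (chapter 10); an alternative LVO share from chapter 1, "since only approximately 7% of these patients have an LVO".

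**Assumptions.** AUC 0.80, the share of patients in Part A, a split proportional by setting where stated, and no known-LVO patients except where stated. The documents give none of these for existing algorithms.

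**The plan's own figure.** 100 LVO / 0.12 = 833.3, rounded up to 834; 834 / 0.70 = 1191.4, rounded up to 1192, as stated. The lower figure comes out at 478 (40 / 0.12 = 333.3, rounded up to 334; 334 / 0.70 = 477.1) against 484 stated, a small difference that does not matter here. The plan states no precision for any AUC.

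**Evaluable patients.** 1192 x 0.70 = 834. Validation set: 0.20 x 834 = 167, about 20 LVO and 147 non-LVO at 12%.

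**Formula (Hanley-McNeil).** With A the AUC, n1 LVO and n0 non-LVO patients, Q1 = A/(2 - A) and Q2 = 2A²/(1 + A):

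SE² = [A(1 - A) + (n1 - 1)(Q1 - A²) + (n0 - 1)(Q2 - A²)] / (n1 n0)

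At A = 0.80, Q1 - A² = 0.6667 - 0.64 = 0.0267 and Q2 - A² = 0.7111 - 0.64 = 0.0711. Intervals are A ± 1.96 SE.

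**All Part A, 50% share** (417 patients, 50/367): SE² = (0.16 + 1.307 + 26.027) / 18350, SE = 0.0387, 95% CI 0.72-0.88.

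**Reading 1: the Part A subset of the validation set, proportional split** (10/73): SE² = (0.16 + 0.24 + 5.12) / 730, SE = 0.0870, 95% CI 0.63-0.97. The ratio is 0.0870 / 0.0387 = 2.25, close to √5 = 2.24, as expected for a fifth of the data.

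**Reading 2: the pooled validation set, as chapter 10 literally reads** (20/147): SE² = (0.16 + 0.507 + 10.382) / 2940, SE = 0.0613, 95% CI 0.68-0.92.

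| Part A share (assumed) | All Part A, LVO/non-LVO | SE, all Part A | Reading 1: SE and factor | Reading 2: SE and factor |
|---|---|---|---|---|
| 25% | 25/184 | 0.0548 | 0.1236 (5/37), 2.26 | 0.0613, 1.12 |
| 50% | 50/367 | 0.0387 | 0.0870 (10/73), 2.25 | 0.0613, 1.58 |
| 75% | 75/551 | 0.0316 | 0.0709 (15/110), 2.24 | 0.0613, 1.94 |

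Under Reading 2 the factor reaches 1 at a 20% Part A share, where all of Part A is as large as the pooled validation set (0.20 x 834 = 167).

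**Sensitivity of Reading 1, 50% share.**
- LVO 7%: 6/77 gives 0.58-1.00 (truncated at 1) and 29/388 gives 0.70-0.90; factor 2.21.
- 10% of Part A known LVO (assumed) and set aside: 9/66 gives 0.62-0.98 and 45/330 gives 0.72-0.88; factor 2.25.
- Simple random split: Part A LVO cases in the validation set follow a hypergeometric distribution (834, 50, 167), mean 10, 95% range 5-16. With 73 non-LVO held fixed, the factor runs from 3.1 to 1.8.
- Only a quarter of the validation set from Part A (5/37): 0.1236 / 0.0387 = 3.19.
- AUC of 0.70 or 0.90 instead of 0.80, proportional split: the factor stays between 2.20 and 2.26.

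**Sensitivity at a cut-off fixed beforehand** (70% assumed, Clopper-Pearson): 7/10 gives 35-93%; 35/50 gives 55-82%. This comparison needs a pre-fixed cut-off, which chapter 10 does not have.

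**The case against.** The strongest reply is that the 2.2 factor is measured against an analysis the plan never defines. Chapter 10 pools the two settings before splitting and does not limit the validation set to Part A. On the literal text the planned interval is 0.68-0.92, not 0.63-0.97, and the factor is about 1.1 to 1.9 over the Part A shares shown. This stands, and both readings have to be reported. The pooled estimate, however, mixes in emergency-room patients, whereas the end point is prehospital.

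A second reply is that chapter 3 already allows the acquired data to be used for validating existing algorithms, and that chapter 10 limits the training of novel algorithms, not the testing of existing ones. This also stands. A reader might infer that the plan forbids fuller use, or that chapters 3 and 10 contradict each other. Neither follows: chapter 3 states a purpose, and chapter 10 describes one evaluation without excluding others. What remains is that no evaluation beyond the validation set is specified.

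Third, a common held-out set is the right basis for comparing existing and new algorithms in the same patients. Agreed; that is a reason to keep it for the comparison, not to confine the stand-alone accuracy estimate to it.

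Fourth, the existing algorithms are unnamed, and any that is re-tuned on study data gains nothing. Also agreed; the point is conditional on that. Finally, because cut-offs are picked on the evaluation data, only the AUC gains directly. The other four measures gain cleanly only if the cut-off is fixed beforehand or cross-fitted.

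**Conclusion.** The point holds as an avoidable loss of precision on a secondary objective, for existing algorithms not trained or tuned on AI-STROKE data. With 834 evaluable patients, 12% LVO and an assumed AUC of 0.80, the standard error is about 2.2 times larger than necessary if the end point is analysed in the Part A part of a proportionally split validation set. It is about 1.1, 1.6 or 1.9 times larger at Part A shares of 25%, 50% or 75% if the pooled set is used, and the pooled figure does not isolate the prehospital setting. The Part A share, the type of split and the AUC are assumptions. If recruitment stops below 1192, the intervals widen on both sides of the comparison, while the proportional-split factor stays near √5.

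A reader might infer that the planned accuracy estimates for existing algorithms are biased by the 20% restriction, or that the primary result is weakened. The documents support neither. A smaller unseen test set is less precise but not biased for that reason, and the primary end point and the criterion of an AUC above 0.80 concern the new algorithms. This is an optional improvement.

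**What to change.** Add to chapter 10 that existing algorithms neither trained nor tuned on study data, listed before analysis, will also be evaluated on all evaluable Part A suspected-AIS patients, training and validation sets together. Report the AUC with a 95% CI. Report sensitivity, specificity, PPV and NPV with 95% CIs at a cut-off fixed beforehand or, where none exists, cross-fitted. Keep the common validation set for the paired comparison with the AI-STROKE algorithms and for any existing algorithm re-tuned on study data.

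The cost is two or three sentences, a cut-off method to specify, and a little more analysis. There is no gain for a re-tuned algorithm, and the gain is smaller if the validation set holds more than a proportional share of Part A.
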